
Planned Sample Size
	
Based on published data, the average pain felt by ladies post uterine artery embolization is 7/10 with a standard deviation of approximately 2.5. The published study of SHGNB for UAE demonstrated a decrease in pain from 7 to 2-5 depending on the analgesics regimen used. We

	
opted for the conservative drop in pain scale from 7 to 5 with a standard deviation of 2.5. This gives an effect size of 0.8. With type I error (alpha) set at 0.05 and type II error (beta) set at 0.2 (power of 80%), the sample size calculations yields a needed sample size of 42. We expect up to a 20% drop out rate due to loss to follow-up, giving a total sample size needed of 50, leaving 25 patients per group.
 
Since the pain drop can be more significant than the conservative value we have opted to use, we suggest an interim analysis that would be expected to give us statistical significance if the pain scale was improved by 50% from 7-3.5 (4 being the number usually used by the recovery room to decide to release patients). Based on similar calculations, to show this level of improvement (taking in account a similar drop out rate), one would need a total of 20 patients and therefore we plan on doing an interim analysis at 20 patients having completed the study to see if there is any need to continue the study or not.

Inclusion Criteria	
 1. Women with symptomatic fibroids or adenomyosis that have requested and been approved for uterine artery embolization 2. Age of patients ranging between 35 and 60 years old 3. Ability to comply with the requirements of the study procedures

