1.3. Pain from Uterine artery embolization

When UAE was first started, the need for pain control was evident. Although it was initially done with general anesthesia in the USA, it was quickly found that this was not necessary. However almost everyone admitted the patient overnight with morphine based patient controlled analgesia (PCA). The use of PCA pumps allowed careful assessment of the pain course after UAE. The information gathered shows a maximal pain threshold reached at approximately 2 hours post-procedure, which lasts 3-4 hours and then a gradual decrease to a lower plateau over another 4-6 hours. This period of decrease to a lower pain plateau is the time during which attempts at discharging the patients from the hospital with oral pain medication is attempted [5]. Most women declare no longer having embolization related pain after 7-10 days.

Because of limited availability to hospital admission after radiological procedures at the MUHC, and the need to offer this less invasive treatment of uterine fibroids to women, the interventional radiologists at the MUHC have offered the procedure with an aggressive IV/Oral sedation protocol while in recovery and discharge orders 4-5 hours after the end of the procedure. The patients are sent home with oral pain medication. However despite this aggressive protocol, approximately 5-10% of patients need admission, not without difficulties at times due to the chronic shortage of beds. This is primarily because this time point of attempted home discharge from the recovery room is still in the phase where the lower more tolerable pain plateau, usually reached only approximately 8 hours after the procedure, has not been reached yet. Even in those that are successfully sent home, they report significant discomfort upon discharge from the hospital and there are some that return to the emergency department for pain management.

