This comparison trial will provide important new information regarding the role SHGNB could play in pain control in women post UAE. The expected benefits would include increasing the availability of UAE in centers with the radiology resources to offer the procedure but without the ability to admit patients overnight and to some patients for whom pain has been a strong deterrent to proceed with UAE and who want to avoid hysterectomy. In addition, another benefit, if proven to allow increased same day discharge, would be to decrease the admission rate post UAE which could have benefits both for the patient as well as for the hospital, in terms of admission bed management, nursing time and medication usage, and at a financial level.

If the procedure is found not to have benefit, this study will give basis to avoid placing patients at risks of complications from an unnecessary added procedure.

5. Data analysis and sample size Calculation

▪ Data gathering and analysis

Nurses in the recovery room will be provided a specific medication escalation regimen to follow based on a patient-centered pain requirement protocol. At the time of discharge, the patient will be seen by the IRMD who will gather the data regarding the dose and frequency of use of analgesia while in the recovery room. He will review the visual analogue pain scale chart with the patient and get her to rank the pain between a scale of 0 to 10 for the pain felt immediately after the procedure, 2 hours after the procedure has ended, and immediately prior to discharge. The recovery nurses will also have a routine pain scale evaluation prior to giving medication and these will be reviewed. The patient will also be given a folder with a series of sheets of visual pain scales to fill out 3 times a day, at specific times while at home, for up to 10 days. They will be provided with a stamped envelope to return to us once they are all filled out. Alternatively, the patient will be offered an anonymous login ID that will allow them to fill out the forms by internet (using a Canadian based survey web site).

The data will be gathered. Confirmation of the data distribution will be done. A normal distribution is expected, but statistical analyses will be modified

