The previous sample size has been calculated with a conservative number, but the decrease in pain can be as large as from 7 down to 2 based on previous studies. Therefore the above estimation may necessitate more patients than are needed to prove clinical worthiness of the procedure. Clinically, our group feels that we would proceed with the block if we could get at least a 50% decrease in pain from 7 down to 3.5 (a scale of 4 being the common number used for discharge of patients from the recovery room). If a similar sample size calculations is performed for such a drop, a total sample size of 16 would be needed. With a similar drop out rate it is our feeling that an interim analysis should be performed at a patient study completion number of 20, so as to avoid recruiting an excessive number of patients to prove the value of the procedure. Therefore we would perform an interim analysis at 20 patients having completed the study. If the data is statistically significant the study would be terminated early.

6. Study Population

The target population who will be included to participate in this study is all women referred to us for a UAE procedure.

6.1. Inclusion criteria:

1. Women with symptomatic fibroids or adenomyosis that have requested and been approved for uterine artery embolization
2. Women age 35-60 y.o.
3. Ability to comply with the requirements of the study procedures

6.2. Exclusion criteria:

1. Patients in whom the vascular anatomy prevents access to the superior hypogastric nerve plexus safely
2. Patients who have known allergy to the anesthetic agent
3. Patients with signs of skin infection at the entry site of the needle used to place the nerve block
4. Patients with signs of infection such as fever
5. Patients with history of inflammatory bowel disease or with signs of colitis
6. Patients with uncorrectable abnormal coagulation status (INR >1.5 and plt < 50000 without use of anticoagulation agents)
7. Patients with preexisting conditions, which, in the opinion of the investigator, interfere with the conduct of the study.
8. Patients who are uncooperative, cannot follow instructions, or who are unlikely to comply with follow-up appointments or fill-out the post-procedural pain questionnaires.
9. Patients with a mental state that may preclude completion of the study procedure or is unable to provide informed consent

6.3. Randomization:

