7.4 Day of the UAE procedure

If consent had not been obtained at the day of the consult because the patient wanted to think about it some more, the patient could be asked at this time whether they want to participate in the study or not. If this is the case, all discussion will occur outside of the angiography room and the patient given information sheet and will be given time to decide whether they would like to participate or not.

If they have decided to participate, a pre-randomized envelope will be opened and will decide whether the patient gets the hypogastric block or the sham procedure. UAE will proceed as per usual. The patient will be recovered for at least 4 hours in the recovery room. Data regarding pain management while in the recovery room will be gathered on the provided information sheets (see appendix). Before discharge, the patient will be seen by one of the interventional radiologists to complete a visual analog pain scale and collect the information that has been gathered. The patient will be provided an anonymization number and reminded to fill out the pain forms at home via hard copy that

she can bring back to us at the time of the follow-up or mail to us (see appendix), or that she can fill out anonymously by internet.

Procedural information will be collected and stored in a secure area for future analysis.

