Appendix III - At discharge from recovery room

Identification code: _____

Date of UAE: _____ (YY/ MM / DD)

RVH/MGH # _____ Age: _____

Pain scale at time of arrival to recovery (0-10): _____ (time: __:__)

IV Medications used during recovery (Dose/ time/pain scale at time of giving it):

Fentanyl (Dose/Time): _____ ug _____:_____ /10
 _____ ug _____:_____ /10
 _____ ug _____:_____ /10
 _____ ug _____:_____ /10
 _____ ug _____:_____ /10

Midazolam (Dose/Time): _____ mg _____:_____ /10
 _____ mg _____:_____ /10
 _____ mg _____:_____ /10
 _____ mg _____:_____ /10
 _____ mg _____:_____ /10

Other (Name/Dose/Time): _____ :_____ /10
 _____ :_____ /10
 _____ :_____ /10

Oral Medications used during recovery (Dose/time/pain scale at time of giving it):

Empracet: _____ / _____ : _____ / _____ /10
 Tramacet: _____ / _____ : _____ / _____ /10
 Oxycodone: _____ / _____ : _____ / _____ /10
 Hydromorphone: _____ / _____ : _____ / _____ /10
 Naprosyn: _____ / _____ : _____ / _____ /10
 Other: : _____ / _____ : _____ / _____ /10
 _____ / _____ : _____ / _____ /10

Pain scale at departure from recovery (0-10): _____ (time: __:__)

Admission to hospital

No Yes - Why: _____

Complications while in recovery: _____

Patient D/C with antibiotics No
 Yes (Name/Dosage/Frequency x # Days)
_____ / _____ / _____ x _____ d

Patient D/C meds: (Name/Dosage/Frequency x # Days)

- Empracet / _____ / _____ x _____ d
- Tramacet / _____ / _____ x _____ d
- Oxycodone / _____ / _____ x _____ d
- Hydromorphone / _____ / _____ x _____ d
- Naprosyn / _____ / _____ x _____ d

Other: _____ / _____ / _____ x _____ d
_____ / _____ / _____ x _____ d
_____ / _____ / _____ x _____ d

Inform patient how to fill out pain scales at home and how to do it by internet. Give out the sheets but encourage using internet if possible and patient at ease with this.

If willing to use internet:

Get patient email address: _____@_____.

Patient anonymous login name: _____

(first letter of hospital/tree numbers in assigned ID code (Ex if first patient enrolled and at the RVH – anonymous ID # is R001))

Give out their login name for the anonymous internet access and write down on hard copy pain scale sheets that go with patient. Give out hard copy sheets even if patient wants to use internet.

Send email immediately to patient to link to internet forms.

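### The discharge pain score is timed by an event that in usual practice depends on the score itself, which attenuates the arm difference at that time point by an unknown amount

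*Combined protocol and SAP*

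**What the plan says.** Section 5 (Data gathering and analysis) has the radiologist ask each patient, at the discharge review, to rate on a 0-10 scale the "pain felt immediately after the procedure, 2 hours after the procedure has ended, and immediately prior to discharge". Appendix III carries the last of these as the line beginning "Pain scale at departure from recovery (0-10", with a space for the clock time.

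Two places link leaving the recovery room to the pain score. The synopsis (Planned Sample Size) describes "4 being the number usually used by the recovery room to decide to release patients". Section 5 (Interim analysis) describes "a scale of 4 being the common number used for discharge of patients from the recovery room". In both, the remark explains the choice of interim effect size. Neither Section 7.4 nor Appendix III states a release score.

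On length of stay, Section 7.4 says: "The patient will be recovered for at least 4 hours in the recovery room". It gives no maximum. Section 1.3 describes current practice as "discharge orders 4-5 hours after the end of the procedure". Of patients sent home it says that "they report significant discomfort upon discharge from the hospital", and it adds that "approximately 5-10% of patients need admission".

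Self-rated pain is a primary outcome (synopsis; Section 3). Section 5 expects a regression of pain over time and names no primary time point, so the departure score can enter the primary comparison.

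**The concern.** An outcome should not be read at a moment chosen partly by its own value. Section 5 gives recovery nurses a medication escalation regimen. A patient above 4 may therefore be medicated and kept longer, and then scored once she is fit to leave. A patient already at or below 4 can be scored as soon as the minimum stay is over. If the block lowers pain, the first course is more common in the sham arm. The arms would then be scored after different waits and different amounts of rescue, and the sham scores would be drawn down toward the release level.

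The design values, 7 and 5, both lie above 4, so the part of the scale where the plan expects the arms to differ is the part that release at 4 would remove. The effect is attenuation: a working block would look weaker at discharge than it is. Section 4 says a finding of no benefit would be grounds for avoiding the procedure, so a bias in that direction matters.

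**Working it through.** **The plan's own figure.** Section 5 uses means 7 and 5 and SD 2.5, so d = (7 − 5)/2.5 = 0.8. A two-sample t-test with alpha 0.05 and 80% power needs 21 per arm, 42 in total, if one-sided. This matches the plan. The two-tailed test named in Section 8 needs 26 per arm, 52 in total. That mismatch is a separate matter; only the means and SD are used below.

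**Assumptions not in the documents.** (a) The 7 versus 5, SD 2.5, applies at 4 hours; the plan attaches no time to these values. (b) Scores are normal, clipped to 0-10. (c) A share h of patients above 4 is held until the score reaches 4. No document gives h.

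**Share above 4 at 4 hours.** Sham: Φ((7 − 4)/2.5) = Φ(1.2) = 88%. Block: Φ((5 − 4)/2.5) = Φ(0.4) = 66%.

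**Means.** Let L(z) = φ(z) − z(1 − Φ(z)). Then L(0.4) = 0.2304, L(1.2) = 0.0561, L(2) = 0.0085 and L(2.8) = 0.0008.

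- Fixed time, sham: 7 − 2.5·L(1.2) + 2.5·L(2.8) = 7 − 0.140 + 0.002 = 6.86.
- Fixed time, block: 5.00, because clipping is symmetric about 5.
- Difference at a fixed time: 1.86.
- All held, sham: 4 − 2.5·L(1.2) + 2.5·L(2.8) = 3.86.
- All held, block: 4 − 2.5·L(0.4) + 2.5·L(2) = 4 − 0.576 + 0.021 = 3.45.
- Difference with all held: 0.42 (from unrounded means).

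Simulation gives the same values.

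**Partial holding.** Difference = (1 − h)·1.86 + h·0.42. The last column averages this with two other in-hospital scores, each assumed to keep 1.86.

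| Share held (h) | Difference in departure score | Average of three in-hospital scores | Loss in the average |
|---|---|---|---|
| 0 | 1.86 | 1.86 | none |
| 0.25 | 1.50 | (1.86 + 1.86 + 1.50)/3 = 1.74 | 0.12/1.86 = 6% |
| 0.5 | 1.14 | (1.86 + 1.86 + 1.14)/3 = 1.62 | 0.24/1.86 = 13% |
| 1 | 0.42 | (1.86 + 1.86 + 0.42)/3 = 1.38 | 0.48/1.86 = 26% |

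**Sensitivity to assumption (a).** If pain has already fallen by 1, 2 or 3 points in both arms, holding every patient above 4 takes the difference from 1.90 to 0.65, from 1.86 to 0.88, or from 1.74 to 1.06. With a larger effect, 7 versus 3.5, it goes from 3.27 to 1.04. The raw difference shrinks in each case and never reaches zero. The spread shrinks too, so the standardised effect falls less: from 0.80 to 0.51 for 7 versus 5 with all held, and from 1.43 to 0.99 for 7 versus 3.5.

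**The case against.** The strongest reply is that 4/10 is not a discharge rule in this protocol. It is mentioned only in passing, as usual practice. Where Section 1.3 describes discharge it does so mainly by time, with orders at 4-5 hours, patients leaving in significant discomfort and only 5-10% admitted. Strict holding at 4 would detain about 88% of sham patients, which fits poorly with that account. This stands: the all-held row is an extreme and h is unknown.

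Arm-dependent timing is also an inference. Section 1.3 puts maximal pain at about 2 hours, lasting 3-4 hours, so until about 5-6 hours. Departures at 4 and at 5 hours would both fall on that plateau. This stands too. Differences in timing matter mainly for patients kept beyond it, and the documents give no distribution of stay.

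Much of the relevant information is already collected. Appendix III records the departure time and the dose, time and pain score at each medication. Analgesic use is itself a primary outcome. This limits the harm but leaves the departure score in the efficacy comparison.

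A reader might infer that this score cannot show a difference between the arms, or that trial power drops to the level computed for this score alone. At 20 per arm, two-sided, that is 69% at a fixed time and 52%, 38% or 35% with a quarter, half or all held. The documents support neither inference. A difference remains in every scenario. The plan specifies no test of this score alone, and expects a regression over time with home scores for up to 10 days.

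**Conclusion.** The point holds in a limited form. The third in-hospital score is timed by an event that in usual practice depends on the score, and the stay has a floor but no ceiling. To the extent that patients above 4 are medicated and kept, the arm difference at that time point is attenuated.

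The size cannot be read from the documents. If 7 versus 5 with SD 2.5 applies at 4 hours, the difference in this score falls from about 1.9 to 1.5 with a quarter held and to 1.1 with half held. The 0.4 with all held is the upper bound on the harm under those values. The average of the three in-hospital scores loses about 6-13% for a quarter to half held, provided the other two scores keep the full difference.

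The 2-hour and home scores are not tied to release. The trial-level effect is therefore smaller than the effect on this one score, and this is a cheap improvement rather than a flaw that undermines the trial.

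**What to change.** In Section 5 and Appendix III, add a self-rating at a fixed 4 hours after the end of the procedure, taken whether or not the patient is ready to leave. The minimum stay in Section 7.4 means patients should still be in recovery then. Use this rating in place of the departure score in the efficacy comparison. Keep the departure score and its already recorded clock time as descriptive data, and compare time to departure between arms as the measure of discharge readiness. No discharge or treatment rule changes.

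The cost is one line on Appendix III, one sentence in Section 5 and one extra 0-10 rating per patient. There is one limit: a fixed-time score removes the dependence on release but still reflects any difference in rescue medication up to 4 hours, so it must be read alongside the analgesic-use outcome.

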Safety	
 ▪ Possible adverse events the SHGNB would include: 
 ▪ Infection ▪ Bowel injury ▪ Vascular injury/Bleeding ▪ Pain or nerve injury ▪ Allergic reaction to the anesthetic agent ▪ Intravascular injection of the anesthetic agent which can lead to cardiac arrhythmias or seizures ▪ Hospitalization or emergent surgery 
The rate of significant complications is estimated to be less than 0.5%.
 
In the sham group, the only significant risks would be infection and allergic reaction to the anesthetic agent.
 
 ▪ Expected possible adverse events of the uterine artery embolization, independent of SHGNB or not 
 ▪ Pain ▪ Vascular injury/Bleeding ▪ Embolization material migrating to non-targeted organs ▪ Premature ovarian failure ▪ Uterine infection leading to possible hysterectomy ▪ Pulmonary Embolus ▪ Leaving a uterine sarcoma unresected 
Other than pain, which is almost universal and premature ovarian failure that can occur in 2-10% of patients, the other risks are in the order of 1-2% or less. Other than pain, it is expected that these complications will be independent of whether a SHGNB is

	
performed or not.
 
Subjects with procedure related adverse events will be followed up until the resolution of the event.
 
A medical monitor will analyze all serious adverse events (“SAE”) in order to confirm that they are unrelated to the research protocol.

Statistical Methods	
Descriptive statistics will be provided for the efficacy outcome results and will be presented in terms of percentage, frequency, means and 95% confidence interval. Differences between both groups will be compared using Chi-square test for categorical variables and, after verifying a normal distribution to the data, a Student’s t- test for the continuous variables. Regression analysis will be performed to compare time dependent events.

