accordingly. We expect that the data analysis will consist of regression analysis of the temporal pain level distribution between the group with and without the SHGNB. Continuous variable data, with normal distributions, subgroup analysis of the secondary objectives will be compared using a Student's t- test.

▪ **Sample size calculation**

Sample size calculations are based on published data showing the average pain felt by ladies post uterine artery embolization being of 7/10 with a standard deviation of approximately 2.5. The published study of SHGNB for UAE demonstrated a decrease in pain from 7 to 5-2 depending on the analgesics regimen used [6]. We opted for the conservative drop in pain scale from 7 to 5 with a standard deviation of 2.5. This gives an effect size of 0.8. With type I error (alpha) set at 0.05 and type II error (beta) set at 0.2 (power of 80%), the sample size calculations yields a needed sample size of 42. We expect up to a 20% drop out rate due to loss to follow-up, giving a total sample size needed of 50, leaving 25 patients per group. [8]

If the analysis of the data after recruiting 50 patients is highly suggestive of an effect but without statistical significance, and if the calculations suggest we could get statistical significance by doubling the number of participants, and there have been no significant adverse events from the nerve block, we would increase the number of patients to 100. If adverse events have occurred, the number would not be increased unless approval by the ethics committee.

▪ **Interim analysis**

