7.5. First 10 days following the procedure

The patient has some pain scoring sheets to fill (3/d for the first three days and the 1/d until day 10 post procedure) which record the amount of pain and the amounts of pain medications used. She can fill them on hard copies provided to her and bring them back at the time of the consult or mail them to us in a prestamped envelope. She can also use a internet anonymous filing system to fill out the forms.

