Data integrity will be maintained throughout the study. Logic rules within the database will be used to maximize integrity, and random data validation checks will be performed routinely. The research investigator will review studies and patients' data on a monthly basis to ensure that patient follow-up is proceeding as expected. All cases where the research investigator finds a discrepancy in imaging interpretation or outcome assessment will be reviewed by the Adjudication Committee, consisting of the principal investigators. An independent radiologist from the MUHC will be asked to determine the outcome of a dispute amongst the Adjudication Committee.

8. Data Analysis:

Data will be collected and tabulated using the commercially available JMP10/SAS statistical analysis software (SAS Institute Inc., Cary, NC, USA). Descriptive statistics will be provided for the efficacy outcome results and will be presented in terms of percentage, frequency, means and 95% confidence interval of the means. Differences between both groups will be compared using the Chi-square test for categorical variables and Student's t- test for the continuous variables. ANOVA test and multivariate logistic-regression analysis will be used to compare interplay of more than two variables. Two-tailed p-values of less than 0.05 will be set for statistical significance.

9. Ethical considerations:

Research Ethics approval from the MUHC Research Ethics Board office will be obtained prior to the commencement of the study or related research procedures. All patients will be informed about the data that will be gathered for the study. All patients will have the ability to refuse participating in the study as soon as they are able to evaluate it and give their approval or not. Patients will always be given options to ask questions at any time and questions will be answered in a non-intimidating way so as to try to avoid influencing the patient's decision. At any time, the patient can decide to remove himself from the study. If this is the case, he will receive the standard of care.

No unique patient identifying data will appear on the sheets that will be coded only by study identification number. A key linking the patient name and study identification number will be maintained in a separate database. All datasheets will be kept in a locked, dedicated research office. All computer records will be maintained in a

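### The primary pain-over-time analysis is an unspecified regression, and no named method is specified as handling 19 to 33 correlated scores per patient

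*Combined protocol and SAP*

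**What the plan says.** Pain on a 0-10 visual analogue scale is a primary outcome, alongside analgesic use (synopsis, Efficacy Outcome; Section 3).

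**Methods named.** Section 5 (Data gathering and analysis) expects "regression analysis of the temporal pain level distribution between the group with and without the SHGNB". The synopsis (Statistical Methods) has only "Regression analysis will be performed to compare time dependent events". Section 8 adds "Differences between both groups will be compared using the Chi-square test for categorical variables and Student's t- test for the continuous variables" and "ANOVA test and multivariate logistic-regression analysis will be used to compare interplay of more than two variables", with two-tailed testing at 0.05. The one flexibility clause, in Section 5, follows a check of the data distribution: "A normal distribution is expected, but statistical analyses will be modified" accordingly.

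**Scores collected.** Section 5 asks for three recovery-room scores: "immediately after the procedure, 2 hours after the procedure has ended, and immediately prior to discharge". For the home diary, Section 5 asks for three scores a day for up to 10 days, while Section 7.5 asks for "3/d for the first three days and the 1/d until day 10 post procedure". Nurses' scores before each dose come on top, in varying number.

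**Decisions that depend on significance.** Section 5 stops the trial if the data are statistically significant once 20 patients have completed. It allows growth from 50 to 100 patients if the result is suggestive but not significant. Neither rule names the test.

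**The concern.** Scores from the same woman are correlated. The chi-square test, t-test, ANOVA and logistic regression assume independent observations in their standard form, and so does an ordinary regression. Each is valid on one value per patient. None is valid on a stack of repeated scores unless the correlation is modelled or the standard errors are corrected. The plan names no mixed model, generalised estimating equations, repeated-measures ANOVA, clustered standard errors or per-patient summary. The flexibility clause deals with distributional shape, not dependence.

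An analyst could therefore follow the text and run a regression on all scores as if each came from a different patient. At the interim look, 20 patients would count as 20 × 19 = 380 to 20 × 33 = 660 independent observations. The resulting p-value could stop the trial early or settle whether it grows to 100.

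**Working it through.** **1. The plan's own figure.** The sample size uses means of 7 and 5 and SD 2.5, so d = 2/2.5 = 0.8, with alpha 0.05 and power 80%. A two-sample t-test at one-sided 0.05 needs 21 per arm, which reproduces the stated 42 (power 81.7%). Two-sided, the total needed is 52, and 42 patients give about 72% power; that is a separate matter. What counts here is that 42 is a number of patients with one score each. The powered comparison is not the comparison over time.

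**2. Scores per patient (m).** Section 7.5: 3 + (3 × 3) + 7 = 19. Section 5: 3 + (3 × 10) = 33, a maximum. Nurses' scores are left out.

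**3. Pooled test of the overall group effect, equal correlation.** The documents give no within-patient correlation (ICC), so 0.1-0.7 is assumed. Pooling understates the variance of the group difference by

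VIF = 1 + (m − 1) × ICC,

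and the true two-sided error of a nominal 5% test is

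2 × [1 − Φ(1.96/√VIF)].

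For example, with m = 19 and ICC 0.3, VIF = 1 + 18 × 0.3 = 6.4, 1.96/√6.4 = 0.775, and the error is 43.8%.

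| ICC | m = 19: VIF, error | m = 33: VIF, error |
|---|---|---|
| 0.1 | 2.8, 24.1% | 4.2, 33.9% |
| 0.3 | 6.4, 43.8% | 10.6, 54.7% |
| 0.5 | 10.0, 53.5% | 17.0, 63.5% |
| 0.7 | 13.6, 59.5% | 23.4, 68.5% |

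These were checked by simulating ordinary least squares on all scores with no true effect (42 patients, 3,000 runs per setting). The simulated rates were 24.0%, 44.5%, 54.3% and 61.1% for m = 19, and 33.2%, 55.5%, 65.2% and 69.0% for m = 33.

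**4. Decaying correlation, and the group-by-time term.** The same simulation was run with correlation falling with time apart (0.1 to 0.7 per day), and with a group-by-time term in the model. Score times were assumed from the two schedules.

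| Test, correlation pattern | m = 19 | m = 33 |
|---|---|---|
| Group effect, decaying | 18-48% | 23-57% |
| Group-by-time, equal | 0.1-4.0% | 0.1-4.3% |
| Group-by-time, decaying | 13-31% | 23-46% |

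Depending on the contrast and the correlation pattern, a pooled test can be far too liberal or too conservative.

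**5. After correction.** A two-sided t-test on one mean score per patient, 21 per arm and 10,000 runs, gave 5.1% (m = 19, ICC 0.3) and 4.7% (m = 33, ICC 0.7). A mixed model was not simulated.

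**The case against.** A reader might infer that the plan commits to ordinary regression on pooled scores, that every listed method treats scores as independent, or that the main test simply has a false-positive rate of tens of percent. The documents support none of these.

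- Section 5 only expects a regression and does not say its type. Regression and ANOVA are families that include mixed and repeated-measures models.
- No section says that repeated scores will be pooled. Section 5 mentions the t-test in connection with subgroup analysis of the secondary objectives, and on one value per patient it is valid.
- The patient is not absent as a unit: the sample size counts patients, 25 per group. That points away from pooling.
- No error rate or correlation appears in the documents. The inflated rates need pooling, an assumed correlation and a particular contrast. At 19 scores under equal correlation, even ICC 0.8 gives 61.7%, so the highest figures belong to the 33-score schedule.
- A comparison over time may well test group-by-time, and that test can fall below 5%.

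All of this stands, and it limits the point to missing specification with a conditional size. It does not remove the point. The wording admits both a valid analysis and a badly invalid one for a primary outcome, and leaves the choice until the data have been seen.

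**Conclusion.** The concern holds as a gap in specification. The primary pain-over-time comparison is an unspecified regression on about 19, or up to 33, scores per patient, and no named method is specified as handling within-patient correlation.

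The size is conditional. If scores were pooled as independent and the overall group effect tested, the two-sided error would be about 24-69% for assumed equal correlation of 0.1-0.7, and about 18-57% if correlation decays over days. The top of each range needs the 33-score schedule. For group-by-time it would be below 5% under equal correlation and about 13-46% under decaying correlation. The simulated figures also assume complete data from 42 patients.

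This is more than missing detail. The listed methods, applied in their standard form to the repeated scores, would give an invalid p-value, and significance governs both the stop at 20 patients and the expansion to 100. It should be corrected before any data are analysed.

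**What to change.** In Sections 5 and 8, and to match in the synopsis, replace the general reference to regression with one of these:

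1. **A linear mixed model** with the patient as the unit, through a random effect or a specified covariance. Include arm, time, arm-by-time and start-of-procedure pain, and name the single primary contrast. A random intercept alone implies equal correlation, so the covariance choice matters for arm-by-time. An unstructured covariance would have 19 × 20/2 = 190 parameters for 19 scores, which is not practical at this sample size.
2. **One pre-defined summary per patient**, for example time-weighted mean pain over a stated window, compared by ANCOVA on start-of-procedure pain. This is the simpler choice for a small trial. State how missing diary entries enter the summary.

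Start-of-procedure pain is already collected in Appendix II, before the block or sham. It serves precision; validity does not depend on it.

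Use the same analysis at the 20-patient interim look, and name it in the stopping and expansion rules. Reconcile the home-diary schedules in Sections 5 and 7.5, since they determine the time points.

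Cost: protocol wording and slightly more analysis work. The JMP/SAS software named in Section 8 can fit either option, and no new data or patients are needed.
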